Address of the place of manufacture: [name], J.S.C. "Biomed"-Mechnikov Tel/[contact], [name]

E-mail: [contact] Internet: www.pharmaclon.ru

Labelling: The inscription "For post-marketing research RAIN-2020" is applied to the primary packaging and secondary (consumer) packaging of the study drug product, the inscription "Not for sale" is additionally applied to the secondary (consumer) packaging in accordance with the requirements of the Federal Law "On Circulation of Medicines" dated 12.04.2010 N 61-FZ as amended Federal Law No. 429-FZ from 22.12.2014.

Compliance assessment

Assessment of compliance with study preventive therapy is evaluated on the basis of data recorded in the participant's diary, on visit 3, as well as in advance as part of an oral survey of the participant on a phone call visit after the end of preventive use of the drug. Compliance is assessed on a 100% scale, where:

100% – participant completed 2 cycles of 10-day courses without violating the dosage regimen and the frequency of admission

90% – participant completed 2 cycles of 10-day courses with a single violation of dosage regimen or dosage frequency

80% – participant completed 1 cycle of the 10-day course without violating dosage regimen or dosage frequency

70% – participant completed 2 cycles of 10-day courses with a double violation of dosage regimen or dosage frequency (single violation of each course)

60% – participant completed 1 cycle of 10-day course with a single violation of dosage regimen or dosage frequency

50% or less – participant completed 1 or 2 cycles of 10-day courses with a systematic (twofold or more) violation of the dosage regimen or dosage frequency in each of the courses (non-compliance with a single dose, frequency of use and/or its duration).

Compliance of 50% or less is the criterion for excluding a participant from the study.

STUDY PARAMETERS OF EFFICIENCY AND SAFETY

Effectiveness criteria

Effectiveness criteria will be evaluated according to the data recorded in the participants' diaries, in primary medical documentation.

Primary effectiveness criterion:

The proportion of patients with acute respiratory viral infections, including COVID-19, at the end of the period of preventive administration of the drug (measurement time: 28 days).

Secondary effectiveness criterion:

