1. The proportion of patients with confirmed COVID-19 at the end of the period of preventive treatment of the drug (measurement period: 28 days).
2. The proportion of patients with acute respiratory viral infections, including COVID-19, at the end of the follow-up period (change period: 2 months).
3. The proportion of patients with confirmed COVID-19 at the end of the follow-up period (change period: 2 months).
4. Frequency of development of complicated course of ARVI.
5. The proportion of participants with each of the scores (0-8) according to the WHO Clinical Improvement Scale (change period: 28 days).
6. The proportion of participants with each of the scores (0-8) according to the WHO Clinical Improvement Scale (change period: 2 months).
7. Duration of symptoms of the disease of study participants who had acute respiratory viral infections, including COVID-19 (change period: 2 months).
8. The duration of the symptoms of the disease of the study participants who were infected with ARVI, including COVID-19 (measurement period: 28 days).

Confirmation of clinical cases of ARVI, including COVID-19:

In the following cases:

- 1) a positive result of PCR on SARS-CoV-2 RNA, regardless of the presence of clinical symptoms;
- 2) appearance of clinical symptoms of ARVI in the absence of a PCR result on SARS-CoV-2 RNA or in the case of a negative result on SARS-CoV-2 RNA, -

at any stage during participation in the study, a completion visit (Visit 3) is conducted at the end of the quarantine period (at least 14 days from the date of signing Consent for the treatment of a new COVID-19 coronavirus infection in outpatient settings (at home) and compliance with the isolation regime or discharge from the hospital in case of laboratory confirmation of COVID-19), at which the patient returns the participant's diary and reports his condition to the doctor-researcher, transmits information about hospitalization, duration of symptoms, results of tests and performed studies.

Definition of the COVID-19 case:

Suspicious case of COVID-19

Body temperature above 37.5° in addition to one or more of the following signs (in the absence of other known causes that explain the clinical picture, regardless of the epidemiological history):

- Cough (dry or with scant sputum)
- Shortness of breath
- Feeling of congestion in the chest
- SpO₂ no more than 95%
- Sore throat
- Nasal stuffiness or moderate rhinorrhea
- Smell disorders or anosmia
- Ageusia
- Conjunctivitis
- Fatigue

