| | there are no clinical or virological signs of infection | no activity restrictions | activity restrictions | hospitalized, no oxygen therapy | hospitalized, oxygen therapy through a mask or nasal cannula | non-invasive lung ventilation or high-flow oxygen therapy | endotracheal intubation and mechanical ventilation | ventilation + additional organ support – pressor drugs, renal replacement therapy, extracorporeal membrane oxygenation (ECMO) | death |

Safety criteria

The assessment of the safety of treatment will be carried out based on registration of adverse events by analyzing complaints and subjective symptoms, comparative analysis of clinically significant changes in laboratory parameters, as well as the severity of these changes, using the CTCAE scale version 4.03 from 2010.

Each participant should be monitored by a researcher for the occurrence of adverse events, which should be classified according to the severity and connection with the drug under study during the entire period of participation in the study.

Adverse events:

Adverse reaction (AR) – an unintentional adverse reaction of the body associated with the use of a drug and suggesting the presence, at least, of a possible relationship with the use of a suspected medicinal product.

Adverse event (AE) – any adverse change in the state of health of the patient or the subject of a clinical trial to whom the drug (study) product was prescribed, regardless of the causal relationship with its use. AE may represent any adverse and unintended change (including deviation of the laboratory indicator from the norm), symptom or disease, the time of occurrence

of which does not exclude a causal relationship with the use of drug product, regardless of the presence or absence of a relationship with the use of drug product¹¹.

Symptoms of acute respiratory infection: fever, manifestations of general infectious intoxication, signs of respiratory damage are not considered as adverse event, however, they are recorded during the study and analyzed as data for evaluating effectiveness.

Assessment of the causal relationship:

Methods for assessing the degree of causal relationship are based on the following criteria:

- the presence of a reliable temporary association of the AE with the use of the study drug (AE are registered after the start of the use of the study drug before the completion of participation in the study);

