2.3. Blinding procedure

This study is open-label.

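### The symptom-only route into the primary endpoint has no threshold in an open-label study, and no sensitivity analysis tests the case definition or masks the arm

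*Protocol*

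**What the plan says.** The primary criterion (Protocol, Effectiveness criteria; SAP 3.1) is "The proportion of patients with acute respiratory viral infections, including COVID-19, at the end of the period of preventive administration of the drug", measured at 28 days.

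Under the heading on confirming clinical cases of ARVI (Protocol; repeated in SAP 3.2), two situations are listed: a positive SARS-CoV-2 PCR with or without symptoms, and "appearance of clinical symptoms of ARVI in the absence of a PCR result on SARS-CoV-2 RNA" or with a negative one. Neither document says which symptoms, how many, how severe or for how long. The nearest description is in the safety section and keeps such symptoms out of adverse event recording: "Symptoms of acute respiratory infection: fever, manifestations of general infectious intoxication, signs of respiratory damage are not considered as adverse event". It names broad groups only.

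COVID-19, by contrast, has explicit criteria. A suspicious case needs a temperature above 37.5 "in addition to one or more of the following signs (in the absence of other known causes that explain the clinical picture". Probable and confirmed cases are also defined.

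On how cases are captured:
- SAP 2.3: "This study is open-label". Group II does not use the drug, and there is no placebo.
- Protocol: "Effectiveness criteria will be evaluated according to the data recorded in the participants' diaries, in primary medical documentation".
- The contact nearest day 28 (Visit 2) is a phone call. PCR is scheduled at Visits 0 and 3 only.
- The study-group diary (Appendix 1) has dated daily pages for days 1 to 9 of each course, each with a symptom prompt. The control diary (Appendix 2), as far as it can be read, has one complaints table for a two-month period.

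The additional analyses of the primary endpoint (SAP 5.4 and 5.5) vary protocol adherence and vaccination status only.

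**The concern.** Participants and investigators both know the arm. With no threshold, whether a mild episode becomes a case depends on the participant mentioning it and the investigator registering it. Either step could be influenced by belief in the drug, by having received nothing, or by how often the diary asks. Neither document describes masked case classification. SAP 5.1 gives data processing to staff who do not manage participants, but that happens after cases are registered.

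The primary comparison is therefore exposed to a registration difference that the planned test cannot separate from a drug effect. Re-running that test in per-protocol or vaccination subsets does not help, because the same cases are counted in the same way.

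**Working it through.** **Inputs from the documents.** 286 per arm to complete and 315 per arm randomized; 1:1 allocation; control incidence 1 to 5%; planned contrast 5% against 2% (Protocol, Number of participants). The test is two-sided at 0.05: Fisher's exact test for expected counts below 5, chi-squared with Yates correction for 5 to 10, plain chi-squared otherwise (SAP 5.1). The Protocol describes a one-sided level; the SAP's two-sided test is used here.

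**The plan's own figure.** With the printed formula and t = 1.96:

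n = (0.05×0.95 + 0.02×0.98) × 1.96² / 0.03² = 0.0671 × 3.8416 / 0.0009 = 286.4, i.e. 286 per arm.

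So 5% against 2% is the scenario behind the sample size.

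**How few episodes matter.** At 5%, 286 × 0.05 ≈ 14 control cases are expected. A split of 14 against 4 gives p = 0.031, so a shift of ten registered episodes is enough.

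**Effect of a registration difference with no true effect.** Let both arms have true incidence p, and let Group I register a fraction r of what control registers. The chance of a significant result favouring the drug is the sum of Bin(a; n, r·p) × Bin(b; n, p) over all pairs (a in Group I, b in control) with a < b and test p-value below 0.05. Exact enumeration at n = 286:

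| Fewer episodes registered in Group I (assumed) | r | Incidence 3% | Incidence 5% |
|---|---|---|---|
| none | 1.0 | 1.6% | 2.4% |
| 20% | 0.8 | 4.0% | 7.9% |
| 30% | 0.7 | 6.2% | 13.3% |
| 40% | 0.6 | 9.6% | 21.2% |
| 50% | 0.5 | 14.7% | 32.1% |

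At 315 per arm and 5%, the range for r = 0.8 to 0.5 is 8.6% to 36%. At 286 per arm and 5%, a 10% difference (r = 0.9) gives only 4.5%.

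**Confining the difference to symptom-only cases.** The table applies it to every case, including laboratory-confirmed ones. Suppose a share f is confirmed and equally captured, and a fraction u of the rest is missed in Group I. Then r = 1 − (1 − f)·u. With f = 0.5 (assumption) and u = 0.2, 0.3, 0.4, 0.5, r = 0.90, 0.85, 0.80, 0.75. The chances at 5% are 4.5%, 6.0%, 7.9% and 10.3%.

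**Power under a stricter case rule.** For a true 5% against 2% at 286 per arm, the SAP test has 46% power. If a fever-based rule keeps 70% of cases (3.5% against 1.4%), power is 28%; if it keeps 50% (2.5% against 1.0%), 17%. Both retention figures are assumptions.

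**The case against.** A reader might infer that the plan has no analysis on an objectively defined case. That is not so. Confirmed COVID-19 at 28 days and at 2 months are secondary endpoints with laboratory criteria and a planned comparison. SAP Tables 9 and 11 also compare a COVID-19 total made up of confirmed, probable and suspicious cases. The suspicious category is close to a fever-plus-sign rule. What stands is narrower. These analyses concern COVID-19, and the suspicious category excludes illness with another known cause, so febrile non-COVID ARVI is left to an unmasked judgement. Nothing links these tables to the primary claim.

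A reader might also infer that most primary events will be symptom-only, or that the bias must favour the drug. The documents support neither. They give no split between COVID-19 and other ARVI. Daily prompts in the study-group diary could raise reporting in Group I and hide a real effect.

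Three further points are fair:
- Cases also come from medical records, and participants are given the doctor's contact details for use when symptoms appear, so the diary is not the only source.
- The lines on confirming cases also set the timing of Visit 3 and are not clearly written as an endpoint rule. But no other ARVI definition exists.
- A programmed rule cannot recover an episode nobody reported, and home temperature is itself self-reported. This limits what the fix can do, but does not remove the gap.

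**Conclusion.** The concern holds as a gap in definition and sensitivity analysis. For a missing or negative PCR, the primary case has no threshold, registration is unmasked, and no analysis of the primary endpoint shows whether the result survives a fixed definition.

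The size is conditional. With no true effect and 286 per arm, an assumed 20 to 50% shortfall in all Group I registrations lifts the favourable false-positive chance from 2.4% to between 8% and 32% at 5% incidence. At 3% incidence it reaches 4 to 15%. It is about 4.5 to 10% at 5% if half the cases are laboratory-confirmed and captured alike. The documents give no reporting rates. The 32% is the upper end of a one-direction scenario, not a forecast. The calculation shows that a reporting difference can produce significance, not that it will.

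**What to change.** Add to the SAP one pre-specified sensitivity analysis of the primary endpoint. Derive the case by program from the recorded data, with the arm code removed. A case is a positive SARS-CoV-2 PCR or antigen test, or a temperature above 37.5 plus at least one sign from the list already used for suspicious and probable COVID-19, whatever the presumed cause. Use the same 28-day window, population and test. Report it beside the any-symptom primary result, and state in advance that a primary effect not seen in it will be interpreted with caution.

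Confirm that the ARVI case registration form mentioned in SAP 5.1 records temperature and signs. Table 9 needs them to classify suspicious cases, but the study-group diary table shows only dates, complaints and therapy. If the form lacks them, add the field.

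The cost is a paragraph of SAP text, one derived variable and possibly one form field. Mild afebrile cases drop out, so this analysis has less power than the primary one. That is a reason to keep it as a sensitivity analysis and not make it the primary definition or require it to be significant. It reduces bias in classifying cases but does not remove bias from episodes never reported.

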For participants who have a case of ARVI (COVID-19), visit 3 can be carried out earlier or later, but the total duration of the study should not be more than 90 days. Up to this point, medical researcher should try to collect the most complete information about the patient's condition. If it is not possible to conduct a face-to-face visit, final visit is conducted remotely.

Schedule of research procedures

| Visit number | 0 | 1 | 2 | 3 |
|---|-----------|---------------|--|--|
| Setting | In person | In person | Phone call | In person |
| Visit name | Screening | Randomization | The end of the course of prevention Beginning of the observation period | End of the observation period Completion of the study |
| Study days | -3-1(0) | 0 | 27 (+/-3) | 56-62* |
| Informed consent ¹ | + | | | |
| Anamnesis ² | + | | | |
| Complaints | + | + | + | + |
| Physical examination ³ | + | + | | + |
| Pregnancy test | + | | | |
| Safety assessment | + | + | + | + |
| Analysis for RNA to SARS-CoV-2 ⁴ | + | | | + |
| Checking the inclusion/non-inclusion criteria | + | + | | |
| Checking exclusion criteria | | | + | |

⁷ A full-time visit can be carried out both at the research center and at home

| | | | | |
|--|---|---|---|----------------|
| Randomization | | + | | |
| Delivery of the study drug ⁵ | | + | | + |
| Compliance assessment | | | + | + |
| Issue of the participant's diary | | + | | |
| Effectiveness evaluation | | | + | + |
| Assessment of the participant's condition according to the WHO scale | + | + | + | + ⁷ |
| Return of study drug and diary | | | | + |

* For patients with a registered case of ARVI, duration of participation in the study may be longer, but not exceed 90 days

- 1 All research procedures, except routine laboratory and instrumental studies, the data of which are used to assess the condition of the study participant, are performed after the procedure of signing the informed consent of the patient
- 2 The study should indicate the epidemiological history of respiratory viral diseases, status of vaccination (influenza, pneumonia, COVID-19), use of means of nonspecific protection and prevention of acute respiratory viral infections, including COVID-19

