In case of a positive PCR test before the start of the drug, volunteer is not included in the study, is isolated and falls under the supervision of a district doctor. In case of a positive PCR test during or after the preventive course, volunteer continues to participate in the study, is isolated under observation and, if possible, comes to visit 3 after the quarantine is lifted (at least 14 days from the date of signing Consent for the treatment of a new coronavirus infection COVID-19 in outpatient conditions (at home) and observing the isolation regime or discharge from the hospital in case of laboratory confirmation of COVID-19) with the provision of data on their condition to the researcher coordinator.

STUDY POPULATION

Adult volunteers who do not have clinical symptoms of ARVI.

Inclusion criteria

1. Volunteers of both genders over 18 years old.
2. Obtaining a written form of informed consent.
3. Ability and consent to participate in this study.
4. No symptoms of respiratory infection.
5. A negative result of a PCR study for the presence of SARS-CoV-2 RNA according to the biomaterial obtained by nasopharyngeal ⁹smear.

Non-inclusion criteria

1. Any other concomitant diseases or conditions that, in the opinion of the research doctor, may distort the results of the study, restrict the rights of the volunteer, or put him at greater risk.
2. Contraindications to the use of the study drug.
3. Individual intolerance of the ingredients included in the composition of the study drug.
4. Pregnancy or breast-feeding.
5. Controversial result of PCR test for the presence of SARS-CoV-2 RNA according to the biomaterial obtained by nasopharyngeal smear.
6. Participation in a clinical trial using the investigated therapy for 30 days prior to inclusion in this study.
7. Disagreement on following reliable contraceptive measures in the framework of the study

⁹ It is permissible to accept the results of a nasal or pharyngeal smear, as well as the results of studies performed before inclusion in the study for no more than 72 hours.

(sexual abstinence; or a combination of 2 different methods: for example, barrier and spermicides, or barrier and intrauterine device, or barrier and hormonal, etc.) – for participants with preserved childbearing potential.

Number of participants

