- Myalgia
- Headache
- Vomiting
- Diarrhea
- Skin rash

Probable case of COVID-19

Body temperature above 37.5° in addition to one or more of the following signs:

- Cough (dry or with scant sputum)
- Shortness of breath
- Feeling of congestion in the chest
- SpO₂ no more than 95%
- Sore throat
- Nasal stuffiness or moderate rhinorrhea
- Smell disorders or anosmia
- Ageusia
- Conjunctivitis
- Fatigue
- Myalgia
- Headache
- Vomiting
- Diarrhea
- Skin rash

In the presence of at least one of the epidemiological signs:

- Return from cross-border travel 14 days before the onset of symptoms
- The presence of close contacts over the past 14 days with a person under surveillance for COVID-19, who subsequently became ill
- The presence of close contacts over the past 14 days with a person who has laboratory confirmed diagnosis of COVID-19

- The presence of professional contacts with persons who have a suspected or confirmed case of COVID-19

Or in combination with characteristic changes in the lungs according to computed tomography (CT), regardless of the results of a single laboratory test for the presence of SARS-CoV-2 RNA and an epidemiological history.

Also, a possible case of COVID-19 should include a clinical case in the presence of the clinical manifestations described above (fever in combination with one or more signs) with characteristic changes in the lungs according to imaging studies if it is impossible to conduct a laboratory study for the presence of SARS-CoV-2 RNA.

Confirmed case of COVID-19

A positive result of laboratory test for the presence of SARS-CoV-2 RNA using nucleic acid amplification methods or SARS-CoV-2 antigen using immunochromatographic assay regardless of clinical manifestations, or a positive result for IgA, IgM and/or IgG antibodies in patients with clinically confirmed COVID-19 infection.

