In the case of ARVI symptoms characteristic of a suspicious case of COVID-19, accompanied by a negative result of PCR test, registered during or after a preventive course (during the period of participation in the study after randomization until the end of the observation period), the patient may additionally undergo a quantitative test for the presence of IgM and IgG antibodies to SARS-CoV-2 by the ELISA method for the purpose of additional verification and detection of COVID-19 cases. An additional quantitative test for antibodies to SARS-CoV-2 can be performed from the 10th to the 21st day after the appearance of the first symptom of ARVI to register the immune response of the acute phase of infection at the beginning of its development (increased IgM levels) or during high-grade response (increased IgM and IgG), considering the seronegative the period of the disease (5-7 days). The analysis is taken only in the absence of fever and a satisfactory general condition of the patient, accompanied by a favorable recovery dynamics. When interpreting the results, it is necessary to consider the probability of obtaining false positive results (for example, the presence of "cross-reacting" antibodies). If the interpretation of the results is difficult, it is allowed to conduct a repeated ELISA study using the same test systems after 5-7 days to assess the dynamics of indicators. Quantitative determination of IgM and IgG antibodies in the blood by the ELISA method will be carried out with the support of DiaLab LLC Plus."

The condition of the study participant is assessed according to the WHO standard scale of clinical improvement from 0 to 8 points at each visit, including a phone call visit. In case of registration of ARVI at the final visit 3, in parallel with the current assessment of the participant's condition, an additional assessment of the case is carried out according to the WHO scale, reflecting the maximum clinical manifestation of the disease.

WHO Clinical Improvement Scale

| Assessment on the WHO scale | 0 | 1 | 2 | 3 | 4 | 5 | 6 | 7 | 8 |
|--|---|--------------------------|-----------------------|---------------------------------|--|---|--|---|-------|
| Select the appropriate score from 0 to 8 | Not infected | Outpatient | | Hospitalized with mild form | | Hospitalized with severe form | | | Died |

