5.4. Deviations from the protocol and the original statistical plan

An additional analysis is planned for the sensitivity of the results of the evaluation of the primary endpoint, depending on the vaccination status.

To maintain the balance and comparability of the groups, as well as to exclude the influence of the period of active antibody formation caused by the vaccine ⁸on the results, as part of an additional analysis, a subpopulation of participants vaccinated with at least one dose of the drug during participation in the study will be excluded from both groups.

⁸Due to the small proportion of vaccinated participants, the number of doses of the vaccine received by the participant and its type (trade name) will not be taken into account

Participants vaccinated prior to inclusion in the study will be included in a modified sample with the formation of a separate population "not vaccinated during the study" to achieve the necessary statistical power.

The conditions for the uniform distribution of patients by vaccination status between groups will be checked beforehand.

All changes in the initial statistical plan with their justification will be reflected in the final report on the clinical trial.

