Thus, the safety population will be used to present demographic data about participants, as well as for safety assessment. ITT will be considered the main sample for comparative analysis of performance parameters. The PP population will include only participants who completed the study without critical deviations from the protocol and will be formed as an additional sample to evaluate the effectiveness parameters in order to analyze the sensitivity of the results obtained in the ITT population. The modified populations will be used to perform sensitivity analysis when evaluating the primary endpoint.

The number of participants who must complete the study in accordance with the protocol is 286 in each group, or a total of 572 participants.

The number of randomized participants is 315 in each group or total of 630 participants.

The number of screened participants is up to 642.

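### Confirmed COVID-19 can rest on a positive IgG without IgM or a rise, with no baseline serology, so old or vaccine antibodies can misclassify cases in secondary endpoints 1 and 3

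*Protocol*

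**What the plan says.** The Protocol (Definition of the COVID-19 case) sets out three classes: suspicious, probable and confirmed. A case is confirmed by a positive nucleic acid or antigen test, "or a positive result for IgA, IgM and/or IgG antibodies in patients with clinically confirmed COVID-19 infection". SAP 3.2 uses the same words.

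The paragraph that follows, also repeated in SAP 3.2, allows an IgM and IgG ELISA in a participant with symptoms of a suspicious case and a negative PCR. It may be done from day 10 to day 21 after the first symptom. Its purpose is to register an early response ("increased IgM levels) or during high-grade response (increased IgM and IgG"). The paragraph says that false positives must be considered, giving cross-reacting antibodies as an example, and permits a repeat ELISA after 5-7 days if interpretation is difficult.

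At entry, the criterion on infection is "A negative result of a PCR study for the presence of SARS-CoV-2 RNA", together with absence of symptoms. Neither previous COVID-19 nor vaccination appears among the non-inclusion criteria. The only SARS-CoV-2 test in the Schedule of research procedures is "Analysis for RNA to SARS-CoV-2", at Visits 0 and 3. Note 2 to the schedule asks for the history of respiratory viral diseases and the "status of vaccination (influenza, pneumonia, COVID-19".

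SAP 5.4 states "Participants vaccinated prior to inclusion in the study will be included in a modified sample". It also removes, in an additional analysis, participants vaccinated during the study, in part "to exclude the influence of the period of active antibody formation caused by the vaccine". SAP 5.5 limits these sets: "The modified populations will be used to perform sensitivity analysis when evaluating the primary endpoint".

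**The concern.** The case definition and the ELISA paragraph do not agree. The first accepts IgG by itself as confirmation. The second does not describe IgG by itself as a sign of acute infection. IgG without IgM, in one sample and with no earlier sample for comparison, does not separate a new infection from a past one or from vaccination.

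The SAP recognises that vaccine antibody formation can influence results, but it applies the vaccination-restricted sets only to the primary endpoint, which does not depend on serology. Confirmed COVID-19, where an antibody result can decide the classification, is planned only in the ITT and PP sets (SAP Tables 9 and 11).

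At stake are secondary endpoints 1 and 3, confirmed COVID-19 at 28 days and at 2 months. If they include illnesses caused by other viruses in people who already carried antibodies, they do not measure what they are named for.

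**Working it through.** **1. Does the text allow the misclassification?**

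| Step | What the documents provide |
|---|---|
| Antibodies present at entry | Possible: previous infection and vaccination are not exclusions |
| Antibodies acquired from a vaccine during the study | Possible: SAP 5.4 plans for such participants |
| Baseline sample for comparison | None scheduled |
| Illness that can lead to the ELISA | Suspicious case: temperature above 37.5° plus at least one listed sign (nasal stuffiness is one), no other known cause, negative PCR |
| Antibody result that confirms | Any one of IgA, IgM, IgG; no titre, rise or second sample required |
| Rule that would reverse it | None: the false-positive caution and the repeat ELISA are left to judgement |

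No step is blocked. The primary endpoint is not touched, because symptomatic ARVI counts whether PCR is absent or negative, whatever the serology shows. In Tables 9 and 11 a suspicious case that becomes confirmed stays within the COVID-19 total; it is the confirmed row, which secondary endpoints 1 and 3 need, that changes.

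**2. Planning figures used for scale.** The Protocol (Number of participants) gives n = t²(P₁Q₁ + P₂Q₂)/(P₁ − P₂)². With P₁ = 0.05, P₂ = 0.02 and t = 1.96:

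n = 3.8416 × (0.0475 + 0.0196)/0.0009 = 286.4, which reproduces the stated 286 per group.

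The planned ARVI totals, COVID-19 included, are then 0.05 × 286 = 14.3 control and 0.02 × 286 = 5.7 study participants.

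**3. Control-arm illustration.** Assumptions, not in the documents: a true COVID-19 rate of 1-2%, seropositivity at entry of 10-30%, and every other ARVI febrile, PCR-negative and tested.

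- True cases: 0.01 × 286 = 2.9 to 0.02 × 286 = 5.7, about 3 to 6.
- Other illnesses: 14 − 6 = 8 to 14 − 3 = 11.
- False confirmations = seropositivity × other illnesses.

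| True cases | Other illnesses | False at 10% | False at 30% | False share of confirmed |
|---|---|---|---|---|
| 6 | 8 | 0.8 | 2.4 | 0.8/6.8 = 12% to 2.4/8.4 = 29% |
| 3 | 11 | 1.1 | 3.3 | 1.1/4.1 = 27% to 3.3/6.3 = 52% |

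These are upper-end counts for the chosen seropositivity, because testing is optional and not every ARVI is febrile. If half the other illnesses were tested, they would halve.

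**4. Direction.** Observed rate = true rate + seropositivity × rate of other tested illnesses.

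- *Real effect on COVID-19, none on other viruses.* True rates 2% and 1% (risk ratio 0.50), other illnesses 3% in both arms. At 10%: 2.3% and 1.3%, ratio 0.57. At 30%: 2.9% and 1.9%, ratio 0.66. The effect is diluted.
- *No effect on COVID-19, effect on other viruses.* True rate 1% in both arms; other illnesses 5 − 1 = 4% and 2 − 1 = 1%. At 10%: 1.4% and 1.1%, ratio 0.79. At 30%: 2.2% and 1.3%, ratio 0.59, against a true ratio of 1. An apparent effect is created.

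**The case against.** The strongest objection is that antibodies never confirm a case alone. The same sentence requires a clinically confirmed illness. If that means a probable case, with an epidemiological link or CT changes, far fewer illnesses qualify. Even a suspicious case needs fever, a further sign and no other known cause. A reader might infer that any febrile cold can become confirmed COVID-19; the documents do not support that. What stands against the objection is that the term is undefined, and that the ELISA is offered to suspicious cases.

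The ELISA paragraph can also be read as guidance that IgG alone would not normally be taken as acute, and history and vaccination status are on record for review. That is a fair reading, but it is not a rule, and the definition says otherwise. The IgA part is largely theoretical: the study ELISA measures IgM and IgG, so IgA could come only from outside testing.

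On vaccination, footnote 8 in SAP 5.4 calls the vaccinated proportion small. This limits the vaccine route but says nothing about earlier infection.

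A reader might also multiply seropositivity by the full 14 and 6 planned illnesses. Those are totals for all ARVI including COVID-19, so they cannot all be PCR-negative non-COVID illnesses. Nor do the documents show that a drug active only against other viruses would be declared effective against COVID-19. In the last scenario above, about 6 against 4 confirmed cases of 286 per arm gives a two-sided Fisher p of about 0.75. Testing is optional and the study open-label, so uptake could differ by arm, but nothing in the documents shows that it would.

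**Conclusion.** The point holds for secondary endpoints 1 and 3 only. The definition lets IgG without IgM or a rise confirm a case, which conflicts with the ELISA paragraph, and nothing in the plan separates old or vaccine antibodies from new ones. The size cannot be derived from the documents. With 10-30% seropositivity and full testing, both assumed, 0.8 to 3.3 false control cases would stand beside 3 to 6 true ones; with few antibody carriers or little testing, the number would be negligible. The bias may dilute a real effect or create an apparent one, depending on how other illnesses split between the arms. The conclusion is that the two endpoints are open to misclassification, not that a false positive trial result is likely. It should be corrected, but it does not threaten the primary analysis.

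**What to change.** - In the Protocol definition and SAP 3.2, confirm a case on PCR or antigen, or on positive IgM or a documented antibody rise between two samples in a suspicious or probable case. State which of these classes the clinical condition means, and state in advance what counts as a rise.
- Do not confirm on IgG or IgA alone.
- For anyone given a vaccine dose during the study, do not confirm on serology at all, since IgM or a rise may come from the vaccine.
- Add a PCR/antigen-only analysis of secondary endpoints 1 and 3, and split the confirmed rows of SAP Tables 9 and 11 by route of confirmation.
- Report the present definition as a sensitivity analysis, with the number of participants ELISA-tested in each arm.

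The cost is wording and re-tabulation of data already collected. No baseline sampling is needed, and the repeat ELISA that would show a rise is already permitted. The downside is the loss of a few true cases tested late or only once.
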